month date. A reminder post card to return the survey will then be sent to non-responders at about 14 days after the survey was mailed. At the 6-month time point, a second cover letter and survey will be mailed to non-responders about 3 weeks after the initial mailing. Study staff (study coordinator and/or RAs) will follow-up with phone calls to answer any questions and offer to do the survey over the phone if the participant prefers. The participant's surveys (screening, baseline, 3 & 6 month) will only be identified by a subject ID number. Data from non-enrolled patients will be immediately stripped of personal identifiers and will not be used in any other analyses. (The screening data will allow for comparison of enrollees with those patients who were ineligible or refused participation, and will enable the detection of inclusion biases.)

If randomization is delayed after receipt of completed baseline survey (e.g., due to staffing issues), participants may no longer be eligible (e.g., their pain has diminished beyond the eligibility threshold), so these particular participants will be called again. Trained interviewers will use a script to 1) remind the participant about the study and review the purpose and what is involved; 2) ask if they are still interested in participating; 3) go through the eligibility questions again if they are interested. If they are no longer interested, these people will not be contacted again. If they are interested and eligible so far, they will be mailed another baseline survey and will receive another \$20 for completion. Upon baseline return, if originally contacted prior to Amendment 8 approval, which added a chart review step to determine eligibility, they will be randomized and treated the same as all other participants from pre-Amendment 8 approval for the duration of the study. Upon baseline return, if originally contacted after Amendment 8 approval, a medical chart review will determine whether they are eligible, and they will be treated the same as all other participants from post-Amendment 8 approval for the duration of the study. If they are interested but no longer eligible based on their answers to the screening questions, study staff will apologize and explain the situation. These people will not be contacted again.

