After completing the baseline survey, study staff will conduct a chart review to determine eligibility (see 5.4 Inclusion/Exclusion criteria for more details), and eligible patients will be randomly assigned to the Usual Care (UC) or Intervention Condition (IC). We will continue to contact patients until we have our required sample of 500 eligible patients (250 in each arm); we are aware that we may need to contact more black than non-black patients due to the likelihood of lower response rates among blacks. Intervention participants will be invited to participate in the 6-session intervention, a pedometer-mediated walking intervention that incorporates Action Planning and MI and Motivational and Cognitive techniques. Patients in the UC condition will receive an informational brochure and a pedometer. The Primary Outcome, pain-related physical functioning, and other pain domains recommended by the Initiative on Methods, Measurement, and Pain Assessment in Clinical Trials (IMMPACT), psychological mediators, and measures of utilization, provider, and environmental factors, and current treatment for pain (pain related services and use of opioid analgesics) will be measured at baseline survey. Baseline data on utilization of health care services, prescription for pain medications, medical comorbidities, and demographic information will be obtained from the Corporate Data Warehouse (CDW) data. We will survey patients by mail (at 3 months and 6 months post-baseline) to assess the same pain measures and psychological mediators that we assessed at

baseline, and assess walking, in the form of daily step counts measured through patient logs of pedometer readings. We will also assess service utilization and opioid analgesics, using data from the CDW and survey data. Data analysis of primary aims will follow intent-to-treat methodology. During Phase 3, we will also conduct analyses of intervention processes using the RE-AIM framework.

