Our sample size calculation was based using the Roland Morris Disability Questionnaire (RMDQ) score as the primary endpoint. For our primary analysis we use a responder analysis, in which we define clinical significant changes as a 30% reduction in pain disability from baseline, using the RMDQ, and have powered the study to be able to detect this change. This is the accepted threshold for clinically significant improvement in clinical trials and recommended by the IMMPACT guidelines and studies demonstrate that a 30% reduction on the RMDQ is a clinically important difference.^{96,97} Prior studies have shown that 15-20% of usual care patients will demonstrate a 30% reduction in pain function score (using the RMDQ and similar measures) from baseline to follow-up, so in order to detect an absolute difference to 20% in the primary outcome measure between treatment groups (i.e. 15-20% in the usual care group compared with 35-40% in the intervention group), we estimate that we will need between 86-97 people in each group with complete data. This estimate takes into account that we are setting the alpha error rate to look separately at both black and non-black patients. We will use the between-group change on the RMDQ as a secondary measure.

We also need to factor in that up to 50% of the study sample may be non-black, since we want to be able to have power to detect meaningful effects in the subgroup that only includes black patients (~100/50%=200). To allow for up to 20% attrition, we would need to randomize 250 patients for each arm of the study, for a total of 500 patients recruited, and 200 black patients with complete data for the final analyses. We estimate that in order to reach a total of 500 patients randomized, we will need to enroll (i.e. participants who are eligible after the phone screener is completed and are thus mailed a baseline survey packet) as many as 1500 patients. Once we reach the goal of randomizing 500 participants, we will stop enrollment.

Risk vs. Potential Benefit

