- The primary analyses for these aims will be conducted in the sample of black patients, so the focus of much of the methods speaks to this primary sample. However, it needs to be clear that the study is designed to be adequately powered to detect effects separately in both the black and non-black groups. This is important from an implementation standpoint since if this intervention is successful it will be important to know whether the effects generalize to a non-black population.

- General Analytic Approach.** These analyses will proceed in three phases. In the first phase (data verification), we will examine the distribution of all study variables to assess extreme values, missing data, variances, skewness, and type of distribution. Frequency distributions and descriptive statistics for all study variables will be computed prior to conducting any analyses. Should normality tests indicate evidence of non-normality for any of our variables (e.g., pain severity ratings) we will compute necessary data transformations. In the second phase, we will evaluate bivariate associations between patients' experimental condition and the outcomes, as well as between each covariate and the outcomes and between each covariate and intervention. These analyses will be done to determine unadjusted measures of effect and assess possible confounders. In the final phase, we will use generalized regression models to estimate the main effects of the intervention. Because of randomization of treatment assignment, we do not anticipate any imbalances in baseline characteristics between groups, but any differences between experimental arms in baseline characteristics will be included as covariates. Likewise, if we find differences in missing data, multiple imputation methods will be used to explore the impact of the missing data and attempt to adjust for its effects on the intervention's effectiveness.

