- Aims 1a) and 1b)** To compare the effects of the intervention to UC on the IMMEDIATE measures of pain outcomes. The primary measure for these aims is the RMDQ score (i.e. primarily a 30% reduction from baseline and secondarily mean change from baseline), and the other secondary measures are pain intensity, the Profile of Mood States, and the global rating of change scale. Analytic approaches for all of these measures will be similar with the exception that some of the measures are dichotomous (i.e. did the participant have a 30% reduction in RMDQ) while other outcomes are assessed on a continuous scale. For all of these outcomes we will use generalized linear regression fit using appropriate distribution and link functions (i.e. for the primary outcome of whether the patient's RMDQ improved by 30% or more we will fit a binomial distribution and logit links, whereas for the comparison of mean differences between treatment groups we might fit a normal distribution). We expect the RMDQ score to decrease (indicating improvement) in the short term (3-month) as well as over the longer term (6-month) in the intervention group, while improving only slightly from baseline in the control group. For continuous outcomes in this model, for example the RMDQ, scores from both 6 months and baseline will be used as the dependent variable, and the independent variables will include the indicator for the intervention group and an interaction term of 6-month time by intervention group indicator. Each participant will be modeled as a random intercept to allow within-patient correlation of the repeated measures. The model can also include other baseline covariates such as age and pain intensity. The use of a mixed-effects model, rather than using multiple linear regression or analysis of

covariance with change-scores or the 6-month values as the dependent variable, will allow us to use data from participants who may be missing either baseline or the 6-month data while giving an unbiased estimate of the outcome comparisons as long as missing-ness is approximately random. The 3-month effect will be similarly assessed.

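### The binary primary endpoint has only a conditional missing-data rule; one unconditional imputation rule with a tipping-point analysis by arm would be better and cheap

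*Combined protocol and SAP*

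**What the plan says.** The primary analysis is a responder analysis: a 30% fall in RMDQ from baseline, compared between arms in black participants (Section 5.1, Power and sample size; Section 5.6, Primary Aim). For this outcome Section 5.6, Aims 1a and 1b, says "we will fit a binomial distribution and logit links".

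The same paragraph then describes a random-intercept model, introduced by "For continuous outcomes in this model, for example the RMDQ, scores from both 6 months and baseline will be used as the dependent variable". Its stated advantage is that it "will allow us to use data from participants who may be missing either baseline or the 6-month data", provided missingness is approximately random. Mean RMDQ change is a secondary measure.

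The only other rule is under General Analytic Approach: "if we find differences in missing data, multiple imputation methods will be used to explore the impact of the missing data and attempt to adjust". What would be adjusted is the estimate of effectiveness. The sentence before it concerns baseline differences between arms.

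On expected loss, Section 5.1 says "To allow for up to 20% attrition, we would need to randomize 250 patients for each arm of the study".

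**The concern.** A responder status needs both a baseline and a follow-up RMDQ score. The random-intercept model works on scores and on secondary outcomes, so it does not supply missing responder statuses. That leaves the conditional sentence as the only missing-data rule for the primary result.

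That rule has two weaknesses. Whether it operates is decided after the data are seen, with no metric or threshold, and the plan does not say whether the imputed result would replace or only accompany the unadjusted one. Also, if the comparison is of missingness rates between arms, it answers the wrong question: two arms can each lose 20% while the patients lost differ in prognosis. Real differences in rate are also easily missed. With 125 per arm, a two-sided 0.05 test of 15% v 25% missing has 51% power.

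If imputation is not triggered, the logistic fit would presumably use only participants with a score. At stake are bias in either direction and a primary result whose adjustment was not fixed in advance.

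**Working it through.** **Inputs from Section 5.1, Power and sample size.** Response 15–20% in usual care and 35–40% in the intervention arm; 86–97 per group with complete data; up to 50% non-black; up to 20% attrition; 250 per arm.

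**Assumptions.** Neither alpha nor power is given as a number; the text says only "This estimate takes into account that we are setting the alpha error rate to look separately at both black and non-black patients". The time point of the binary endpoint is not fixed; 6 months is assumed. The pattern of loss is not given, so a range is shown.

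**1. Reproduce the plan's sample size.** n = 2(z_α/2 + z_β)²/h², with h = 2·asin√p₂ − 2·asin√p₁.
- Two-sided 0.025, 80% power: 85.8 (15% v 35%) and 97.2 (20% v 40%), matching 86–97.
- Two-sided 0.05, 80% power: 70.9 and 80.3, which do not match.
- Inflation: 100/0.50 = 200; 200/0.80 = 250 per arm. At a 50% share, that is 125 black participants randomised and 100 complete per arm.

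The sample size is not at fault, and 0.025 is the alpha that its figures imply.

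**2. Observed-case bias with no true effect (20% response).** If a fraction m is lost and those lost respond at rate r, the observed rate is (p − m·r)/(1 − m). Rejection rates use the unpooled normal approximation at two-sided 0.025.

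| Loss per arm | Informative in | r | Difference (points) | False positives |
|---|---|---|---|---|
| 20% | neither arm, or both equally | – | 0 | 2.5% |
| 20% | intervention only | 10% | (.20−.02)/.80 − .20 = +2.5 | 3.9% |
| 20% | intervention only | 0% | .20/.80 − .20 = +5.0 | 8.3% |
| 10% | intervention only | 10% | (.20−.01)/.90 − .20 = +1.1 | 2.8% |
| 10% | intervention only | 0% | .20/.90 − .20 = +2.2 | 3.7% |

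If only usual-care loss is informative at 20%, the bias is −2.5 or −5.0 points.

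**3. Power at a true 40% v 20%, 20% lost, 100 observed per arm.** With uninformative loss, power is 82%. With informative usual-care loss only, usual care appears to respond at 22.5% or 25.0%, the difference shrinks to 17.5 or 15.0 points, and power falls to 68% or 52%.

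**4. Tipping point.** 25 missing per arm; missing usual-care patients respond at 20%, so usual care is 25/125. Let k of the 25 missing intervention patients respond. Unpooled z test on 125 per arm.
- Observed 35 v 20 of 100 (observed-case p = .016). k = 5: 40/125 v 25/125, difference .12, SE √(.32×.68/125 + .20×.80/125) = .0550, z = 2.18, p = .029. k = 6: p = .020. k = 4: p = .041. k = 3: p = .056. Significance is lost at k ≤ 5 for alpha 0.025, and at k ≤ 3 for alpha 0.05.
- Observed 40 v 20 of 100. k = 0: p = .029. k = 1: p = .020. It is lost only at k = 0 for alpha 0.025, and never at 0.05.

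**5. What imputation can recover.** Illustrative rates, not from the plan: no true effect; 20% respond at 3 months; 6-month response is 60% in 3-month responders and 10% in the others; the intervention arm loses 20%, all 3-month non-responders; usual-care loss is random. The observed-case intervention rate is (.12 + .06)/.80 = .225, a bias of +2.5 points. Imputation by arm gives:
- all missing patients have a 3-month score: .18 + .20×.10 = .200, bias 0;
- half have one: .18 + .10×.10 + .10×.211 = .211, bias +1.1;
- none has one: .18 + .20×.225 = .225, bias +2.5.

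**The case against.** **The rule already aims to adjust.** This stands. The conditional sentence names adjustment as a purpose, so calling it merely exploratory would be unfair. The link to the preceding sentence also makes between-arm differences the natural reading. What is missing is the metric, the threshold and the standing of the adjusted result.

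**The trigger might already catch the illustrated case.** This stands in part. If it covers the pattern of missingness as well as its rate, the loss in step 5 could set off imputation under the current plan. The gain shown there is a gain over an observed-case fit. It is a gain over the plan only if the trigger compares rates.

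**The harm needs one-sided informative loss at the attrition ceiling.** This is true of the null bias, and at 10% loss the inflation is slight. The planned 20-point effect is fairly robust.

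**Retention effort is substantial.** Reminder postcards, telephone completion and payment for each survey apply at both follow-ups (Sections 5.1 and 5.2), although the repeat mailing is described for one: "At the 6-month time point, a second cover letter and survey will be mailed to non-responders about 3 weeks after the initial mailing". These measures reduce loss but are not analysis rules.

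**Stronger readings that the documents do not support.** A reader might infer that the plan prescribes a complete-case analysis; it states no such rule. A reader might see a breach of "Data analysis of primary aims will follow intent-to-treat methodology"; Section 5.6 defines this as analysis by assigned group, which missing scores do not breach. A reader might think Section 5.7 contradicts that commitment by allowing termination from the study; it is only silent on whether outcomes are still collected, and Section 5.5 refers to supporting documents that were not available.

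**Conclusion.** The point holds as a cheap improvement to the analysis plan. The sole missing-data rule for the primary endpoint depends on the data and is not fully specified, so an unadjusted observed-case result could stand as primary at up to 20% loss.

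The size depends on the loss mechanism. It ranges from no bias to 5 points either way under the null at 20% loss, with false positives up to 8.3% against 2.5%, or power down to 52% against 82%. These figures rest on the inferred alpha of 0.025, 125 black participants per arm, a 6-month endpoint and assumed response rates among the missing.

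It would be too strong to say that an observed 35% v 20% loses significance whenever missing intervention patients respond at the usual-care rate. That holds at alpha 0.025 (p = .029 at 5 of 25) but not at 0.05. Nor does imputation by itself remove the bias: it cannot correct loss that depends on the unseen 6-month score. Only the tipping-point analysis shows how much that would matter.

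**What to change.** In Section 5.6:
- Delete the conditional trigger. Define the primary analysis as all randomised black participants by assigned arm, and name the time point.
- Multiply impute RMDQ unconditionally, by arm, from baseline RMDQ, the other follow-up score and baseline covariates. Derive the 30% responder in each imputed set, pool the logistic results, and state the missing-at-random assumption.
- Prespecify a tipping-point analysis that varies the response of missing patients separately by arm.
- Report by arm how many of those missing at 6 months have a 3-month score.
- Use the same rule for non-black participants (Secondary Aim 3).

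The cost is SAP wording and modest programming, with no change to sample size. The estimate may be less favourable and the intervals wider. Imputation gains little over the observed-case fit if few of those missing at 6 months have a 3-month score or if loss depends on the unseen 6-month score. It gains less over the current plan if the present trigger is read to cover patterns of missingness.

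As a separate clarification, Section 5.7 should be read together with the intent-to-treat statements in Sections 5.1 and 5.6, and the plan should say whether outcomes are collected after termination.

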- We will assess the time-averaged effect of the intervention on pain-related functional interference and the outcome trends over time using the outcome measures at all three times (including the baseline) as repeated measures nested within patients and using a mixed-effects model. Prior to fitting the mixed-effects model, we will explore the trends graphically by plotting the cross-sectional means of the outcome measures at each measurement time separately by the two study groups. We will also graph the outcome measures by individual participants to assess the participant specific longitudinal pattern over time. The mixed-effects model will be guided by the results of the graphical analyses. For instance, we expect decreasing trends in the outcome measures over time in the intervention group and no particular trends in the control group. If such a pattern is indicated, linear time and an interaction of linear time by intervention group will be included in the model. In this model, if the time variable is not significant and the interaction is estimated with a significant negative coefficient, it would provide evidence for linearly decreasing outcomes (i.e., improvement in function) in the intervention group over the one follow-up period. If, on the other hand, the graphical analyses suggest that the outcomes in the intervention group decrease at 3 months with no noticeable change between 3 to 6 months, we will model this by including time as dummy categorical variables and interaction terms of intervention group by time dummy categorical variables. An appropriate contrast for the covariate adjusted difference in outcome means at 3 months and 6 months between groups will be constructed to estimate and test for the intervention effect. Using this model, mean changes from baseline can also be estimated and tested for each group. If we find no difference in the intervention effect between 3 and 6 months using this model, we will model the post-intervention time together to obtain a time-averaged intervention effect. The mixed-effects models will also include the baseline values of the outcome measure and other baseline covariates to adjust for potential baseline differences between the groups.

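### The 6-month model for continuous outcomes leaves out the 3-month scores, which narrows its missing-data assumption to baseline alone; one pre-specified three-time model would fix this at no cost

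*Combined protocol and SAP*

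**What the plan says.** Section 5.6, Aims 1a) and 1b), sets the model for continuous outcomes. Mean RMDQ change is the lead example and is secondary to the 30% responder analysis. For the 6-month effect, "scores from both 6 months and baseline will be used as the dependent variable", with the covariance given by "Each participant will be modeled as a random intercept to allow within-patient correlation of the repeated measures". The 3-month effect gets a parallel fit: "The 3-month effect will be similarly assessed".

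The stated reason for preferring this model to change-score regression or ANCOVA is that it can use incomplete participants while "giving an unbiased estimate of the outcome comparisons as long as missing-ness is approximately random".

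The 3-month scores exist. Section 5.1 says "We will survey patients by mail (at 3 months and 6 months post-baseline) to assess the same pain measures", and Table 3 schedules RMDQ, PEG, PHQ-8 and GAD-7 at 0, 3 and 6 months.

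The next paragraph of Section 5.6 adds a second model, "using the outcome measures at all three times (including the baseline) as repeated measures nested within patients", for the time-averaged effect and trends. Its form is to follow inspection of plots: linear time if a steady decline appears, or categorical time with 3- and 6-month contrasts if the change occurs by 3 months.

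In Section 5.1, Power and sample size, the allowance for loss is "To allow for up to 20% attrition".

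**The concern.** A likelihood model is protected against dropout only to the extent that missingness is random given the data in the model. With baseline and 6-month scores alone, the chance of a missing 6-month score must be unrelated to its value once baseline is known. If people who are doing badly at 3 months stop responding, that condition fails, even though missingness would be random given everything observed. The model then loses the property for which the plan chose it.

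The three-time paragraph does not settle the matter. It serves other questions, its form depends on the data, and the explicit 6-month contrast is described only in the branch that the plan does not expect. For the mediators, Secondary Aim 1 describes the approach as identical to that of the Primary Aim and ranks the 6-month effect first and trends second. That makes the two-time model the leading one. At stake are the continuous RMDQ result, the continuous H1b measures and the mediators.

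**Working it through.** **The plan's own figure.** No sample size or power is given for the continuous model. The only figure is for the responder endpoint: 86-97 per group with complete data. Alpha and power are not stated. With two-sided alpha 0.025 (0.05 split over two race groups) and 80% power, n = (2.2414 + 0.8416)² × [p1(1−p1) + p2(1−p2)] / 0.20².
- 15% v 35%: 9.505 × 0.355 / 0.04 = 84.4, so 85.
- 20% v 40%: 9.505 × 0.400 / 0.04 = 95.1, so 96.
- The pooled-variance formula gives 88 and 99.

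The stated range is therefore reproduced, and 200 / 0.8 = 250 per arm. It does not bear on this point, except that 250 × 50% gives 125 black patients per arm.

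**Assumed inputs (none is in the documents).** SD 1; correlations r03 = 0.65, r36 = 0.75, r06 = 0.55; 20% of 6-month scores missing, with half to all of that loss after 3 months; log-odds of dropout changing by s per SD of the 3-month score; no true effect.

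**Size of the bias.** Let p be the dropout probability after 3 months among those still responding.
1. The log of the retention probability changes by about −s·p per SD of the 3-month score.
2. Among completers, the 3-month residual given baseline therefore shifts by about −s·p·(1 − r03²).
3. The slope of the 6-month score on the 3-month score, given baseline, is (r36 − r03·r06)/(1 − r03²) = (0.75 − 0.3575)/0.5775 = 0.68.
4. The product is a shift per arm of −s·p·(r36 − r03·r06) = −s·p·0.3925. The bias is the difference between arms.

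With all loss after 3 months, p = 0.20. With half, p = 0.10/0.90 = 0.111. Large-sample random-intercept fits to baseline and 6 months agree with this approximation. Negative values favour the intervention.

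| s, intervention v usual care | Formula, all / half | Simulated, all / half |
|---|---|---|
| 1 v 0 | −0.079 / −0.044 | −0.067 / −0.039 |
| 0.5 v 0 | −0.039 / −0.022 | −0.039 / −0.021 |
| 1 v 0.5 | −0.039 / −0.022 | −0.032 / −0.020 |
| equal | 0 | about 0 |
| 0 v 1 | +0.079 / +0.044 | +0.070 / about +0.04 |

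If only a quarter of the loss follows 3 months, the first three rows fall to −0.025, −0.007 and −0.011. With a true effect of 0.4 SD, equal dependence leaves about 0.02 SD.

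**Adding the 3-month score.** With unstructured covariance, the three-time model's bias is within 0.004 SD of zero in every scenario. With only a random intercept, −0.016 to +0.021 SD remains under these correlations when all loss follows 3 months. Up to 0.04 SD remains under another unequal set (0.6 for 0-3 months, 0.7 for 3-6, 0.5 for 0-6) with opposite dependence in the two arms.

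**Precision under completely random dropout.** The squared partial correlation of the 3- and 6-month scores given baseline is 0.3925² / (0.5775 × 0.6975) = 0.382.
- All loss after 3 months: variance saving 0.382 × 0.20 = 7.6%.
- Half: 0.382 × (1 − 100/112.5) = 4.2%.

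Simulated savings were 4.5-9% for unstructured fits and about 2-6% for random-intercept fits.

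**The case against.** The strongest reply is that the plan already has a three-time model with a possible 6-month contrast, that multiple imputation is planned if missing data differ, and that the unbiasedness statement is conditional. All of that is true, but none of it closes the gap. The contrast depends on what the plots show, the imputation is exploratory and lists no inputs, and the condition is never said to be relative to any particular scores.

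The other objections bear on size, and they stand. Every input to the bias is assumed. Coaching ends at 10-12 weeks (14 at most), survey mailings and reminders do not differ by arm, and the second mailing at 6 months may recover some 3-month non-responders. Anyone already lost by 3 months has no 3-month score to contribute. Intervention participants do keep diaries for 6 months, so a difference between arms is possible, but it is not shown.

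A reader might infer that the bias must flatter the intervention because only that arm is coached. The documents do not support this: if the dependence lies in usual care, the sign reverses. A reader might also take false-positive rates of 8-15% as the likely consequence. Those rates need dropout to run in opposite directions in the two arms, and nothing in the plan suggests that it will.

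Step counts do not belong in this point, because Aim 1c already models them at all three times.

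**Conclusion.** The point holds as a low-cost improvement to a secondary analysis. The two-time model discards collected information that bears directly on the missing 6-month scores, so its assumption is stricter than the plan's wording conveys. The plan also gives two routes to the same 6-month effect without saying which governs.

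Under the assumed correlations and 20% loss, half to all of it after 3 months, the bias is about 0.02-0.07 SD when dropout follows 3-month status in one arm or more strongly in one arm. It can go either way, and it is about zero when the dependence is equal. The standard error at 125 per arm is roughly 0.13-0.15 SD in the simulated random-intercept fits, so this is a fraction of one standard error. The precision gain is about 2-9% of variance. The responder endpoint and the sample size do not change.

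**What to change.** In Section 5.6, Aims 1a) and 1b) and the paragraph that follows, replace the separate two-time models and the plot-driven choice of form with one pre-specified likelihood model for each continuous outcome:
- responses are the baseline, 3-month and 6-month scores;
- time is categorical, with arm-by-time terms;
- covariance is unstructured, because a random intercept alone leaves part of the bias;
- the 3-month, 6-month and time-averaged effects are contrasts from this model.

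Baseline then enters as a response and should not also be a covariate, as the three-time paragraph now has it. State that missing at random is conditional on baseline and 3-month scores. Plots can stay as description.

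The cost is wording in the analysis section. No new data are needed, and one model replaces several.
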